6.1.3 Rescue medication

Not applicable

6.1.4 Guidelines for continuation of treatment

Not applicable

6.1.5 Treatment duration

All patients will begin treatment on Cycle 1 Day 1.

Prior to the primary analysis cut-off date (10-Aug-2018), patients will continue study treatment until disease progression per RECIST 1.1 or irRECIST (see below), **as per BIRC**, unacceptable toxicity, start of new anti-neoplastic therapy, withdrawal of consent, physician’s decision, subject/guardian decision, lost to follow-up, death or the study is terminated by the sponsor. While the investigator is waiting for the results from the central imaging vendor to confirm disease progression, the patient should continue on study treatment. However, during this time, the investigator should do whatever is medically necessary for his/her patient.

After the primary analysis cut-off date (10-Aug-2018):

- Response assessments by BIRC will no longer be performed.
- Patients, who are on treatment but have not yet progressed per local tumor response assessment, will continue study treatment until documentation of disease progression by RECIST 1.1 as per local investigator assessment, unacceptable toxicity, start of new anti-neoplastic therapy, withdrawal of consent, physician’s decision, subject/guardian decision, lost to follow-up, death or the study is terminated by the sponsor. These patients will be permitted to continue study treatment beyond initial PD as per RECIST 1.1 until confirmed irPD per local assessment (until 2 consecutive irPDs), as described in [Section 6.1.5.1](#).
- Patients, who are on treatment beyond disease progression per local tumor response assessment (tumor assessment performed before the primary analysis cut-off date [10-Aug-2018]), are allowed to continue study treatment as long as the patient derives clinical benefit from the treatment according to investigator’s best clinical judgement (e.g. no deterioration of performance status, no rapid increase in tumor burden, no clinical situation requiring alternative treatment), or until unacceptable toxicity, start of new anti-neoplastic therapy, withdrawal of consent, lost to follow-up, death, or the study is terminated by the sponsor.

6.1.5.1 Treatment beyond disease progression

Emerging clinical data indicate that patients may derive benefit from continuing study treatment despite initial evidence of disease progression ([Section 2.5](#)).

Prior to the primary analysis cut-off date (10-Aug-2018), patients treated with PDR001 will be permitted to continue study treatment beyond initial disease progression as per RECIST 1.1 until disease progression per irRECIST, as per BIRC, unacceptable toxicity, start of new anti-neoplastic therapy provided they meet all of the following criteria:

- Absence of disease progression per irRECIST, as per BIRC, confirmed by 2 consecutive assessments
- The continuation of treatment beyond progression will not delay an imminent intervention to prevent serious complications of disease progression
- Patients exhibit adequate tolerance to study treatment
- Patient performance status is stable

Patients who meet the above criteria should continue study treatment beyond initial disease progression per RECIST 1.1 and continue all study procedures as outlined in [Section 7](#). The reasons for the patient continuing treatment will be documented in the eCRF.

In case of clinical deterioration or suspicion of disease progression, a follow-up imaging assessment should be performed promptly rather than waiting for the next scheduled assessment. Treatment with PDR001 in patients who are no longer deriving clinical benefit or have disease progression as per irRECIST by BIRC confirmed by 2 consecutive assessments must be discontinued.

After the primary analysis cut-off date (10-Aug-2018):

- Response assessments by BIRC will no longer be performed.
- Patients, who are on treatment but have not yet progressed per local tumor response assessment, will continue study treatment until documentation of disease progression by RECIST 1.1 as per local investigator assessment, unacceptable toxicity, start of new anti-neoplastic therapy, withdrawal of consent, physician's decision, subject/guardian decision, lost to follow-up, death or the study is terminated by the sponsor. These patients will be permitted to continue study treatment beyond initial PD as per RECIST 1.1 until confirmed irPD per local assessment (until 2 consecutive irPDs) provided they meet all of the following criteria:
 - Absence of disease progression per irRECIST, confirmed by 2 consecutive assessments
 - The continuation of treatment beyond progression will not delay an imminent intervention to prevent serious complications of disease progression
 - Patients exhibit adequate tolerance to study treatment
 - Patient performance status is stable
 - Patients who meet the above criteria should continue study treatment beyond initial disease progression per RECIST 1.1 and continue study procedures as outlined in [Section 7](#). The reasons for the patient continuing treatment will be documented in the eCRF.
- Patients, who are on treatment beyond disease progression per local tumor response assessment (tumor assessment performed before the primary analysis cut-off date (10-Aug-2018)), are allowed to continue study treatment as long as the patient derives clinical benefit from the treatment according to investigator's best clinical judgement (e.g. no

deterioration of performance status, no rapid increase in tumor burden, no clinical situation requiring alternative treatment), or until unacceptable toxicity, start of new anti-neoplastic therapy, withdrawal of consent, lost to follow-up, death, or the study is terminated by the sponsor.

6.2 Dose escalation guidelines

Not applicable

6.3 Dose modifications

6.3.1 Dose modification and dose interruption

For patients who do not tolerate the protocol-specified dosing schedule, dose interruptions are mandated in order to allow patients to continue study treatment. Dose interruption for PDR001 includes delaying or withholding treatment for any reason as well as interrupting treatment during an infusion.

The following sections address specific instructions for mandatory dose modifications and recommended management of adverse events considered suspected to be related to PDR001.

6.3.1.1 Dose modification and dose interruption for PDR001

General dose modification instructions:

No changes in the dose of PDR001 are allowed.

AEs are to be graded according to NCI-CTCAE v4.03 (ctep.cancer.gov). All dose interruptions and the reasons for dose interruption must be documented in the eCRF.

Treatment of patients with AEs suspected to be related to PDR001 including those of potential immune-mediated etiology (irAE) (see definition in [Section 6.3.1.2.1](#)) must be permanently discontinued if the following occurs within 12 weeks:

- AEs do not recover to \leq grade 1 or baseline
- The dose of steroids (for the management of irAEs) is > 10 mg/day prednisone or equivalent (or as indicated in the tables below)

The 12 weeks' period starts from the time an irAE reaches a severity grade that requires PDR001 interruption.

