Grade 1: Rash covering < 10% Body Surface Area (BSA)	
 ● Initiate prophylactic and symptomatic treatment measures. ● Consider use of topical corticosteroids or urea containing creams in combination with oral antipruritics or moderate strength topical steroid (hydrocortisone 2.5% cream or fluticasone propionate 0.5% cream) ● Reassess after 2 weeks. 	Continue PDR001 treatment
Grade 2: 10-30% of BSA	
 ● If tolerable, treat as per Grade 1; ● If intolerable, initiate systemic steroids (e.g. oral prednisolone 0.5-1mg/kg daily) and consider dose interruption until tolerable or recovery to grade ≤1 or baseline; once recovered, resume PDR001 treatment at the same dose and schedule. ● If symptoms persist or recur consider skin biopsy. 	
Continue PDR001 treatment
 
AE resolution to ≤1 or baseline must occur within a period of 12 weeks since Grade 2 event has been identified, otherwise PDR001 must be permanently discontinued.

Grade 3: More than 30% of BSA	
 ● Obtain a skin biopsy and dermatology consult. ● Initiate systemic steroids with 1mg/kg of prednisolone or IV equivalent. 	
1st occurrence:
 
 ● Interrupt PDR001 until rash recovers to Grade ≤1 or baseline ● Once recovered restart PDR001 treatment at the same dose and schedule 
AE resolution to ≤ Grade 1 or baseline must occur within a period of 12 weeks since intolerable Grade 3 event has been identified. Otherwise, PDR001 must be permanently discontinued
 
2nd occurrence: Permanently discontinue PDR001

Grade 4: Life-threatening	Same as Grade 3	Permanently discontinue PDR001
Other skin events		
Stevens-Johnson syndrome and toxic epidermal necrolysis	Institute supportive care as per institutional guidelines	Permanently discontinue PDR001

Table 6-5 Mandatory dose modification requirements and recommended clinical management guidelines for potential immune-related nephritis

Nephritis (NCI-CTCAE v4.03)		
Grade	Recommended Adverse Event management guidelines	Mandatory Dose Modification requirements
Grade 1: Creatinine >ULN to ≤1.5x ULN)	
 • Monitor creatinine weekly • If creatinine return to baseline resume routine creatinine monitoring per protocol • Promote hydration and cessation of nephrotoxic drugs 	Continue PDR001 treatment

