6.3.1.2.2 Guidance for corticosteroids tapering for management of immune-related AEs

Reduce prednisone dose by 2.5- to 5.0-mg decrements every 3–7 days until physiologic dose (5 to 7.5 mg of prednisone per day) is reached. Consider to complete tapering over a period of at least 4 weeks. Slower tapering of corticosteroids therapy may be recommended if the adverse event is not showing improvement. Once corticosteroid tapering is achieved at a level of 10 mg of prednisone/day (or equivalent), treatment with PDR001 can be restarted as indicated in the dose modification tables.

6.3.1.3 Dose modification requirements for adverse events suspected to be related to study treatment

The required dose modification and management of adverse events that are considered to be related to study medication and do not have specific management requirements noted elsewhere in the protocol are provided in [Table 6-11](#) and [Table 6-12](#).

Table 6-11 Mandatory dose modification requirements and recommended clinical management guidelines for hematologic adverse events suspected to study treatment

Hematologic suspected AEs (NCI-CTCAE v4.03)		
Grade	Recommended Adverse Event management guidelines	Mandatory Dose Modification requirements
Neutropenia		
Grades 1, 2	NA	Continue PDR001 treatment
Grade 3, 4	Monitoring blood test more frequently (every 7 days for grade 3, and 3-5 days for grade 4)	
1st occurrence:
 
 Interrupt PDR001 until toxicity recovers to Grade ≤2 or baseline. 
 Once recovered restart PDR001 treatment at the same dose and schedule 
2nd occurrence:
 
 Interrupt PDR001 until toxicity recovers to Grade ≤2 or baseline 
 Once recovered restart PDR001 treatment at the same dose and schedule 
AE resolution to ≤ Grade 2 or baseline must occur within a maximum period of 12 weeks since Grade 3 or 4 event has been identified, otherwise PDR001 must be permanently discontinued
 
3rd occurrence: Permanently discontinue PDR001.

Febrile Neutropenia	Apply Institutional guidelines	Follow- neutropenia Grade 4 requirements (above)
Thrombocytopenia (NCI-CTCAE v4.03)		
Grade 1, 2, 3 without clinical significant bleeding	Grade 3: monitoring blood test more frequently (every 7 days)	Continue PDR001 treatment

Hematologic suspected AEs (NCI-CTCAE v4.03)		

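### The general 12-week discontinuation rule (Protocol 6.3.1.1) and Table 6-11 set different recovery grades for neutropenia and thrombocytopenia, and no order of precedence is stated

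*Protocol*

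**What the plan says.** Protocol 6.3.1.1 gives general instructions for all adverse events suspected to be related to PDR001, immune-related or not. Treatment "must be permanently discontinued if the following occurs within 12 weeks", and two conditions follow. The first is failure to recover to grade 1 or lower, or to baseline. The second is a steroid dose above 10 mg/day prednisone or equivalent, and this one carries a parenthesis pointing to the later tables. A closing sentence says that the 12-week "period starts from the time an irAE reaches a severity grade that requires PDR001 interruption".

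Protocol 6.3.1.2.1 states that the dose-modification column of the tables is mandatory, while the management column is a recommendation that local practice may modify.

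Table 6-11 (Protocol 6.3.1.3) covers suspected hematologic events. For grade 3 or 4 neutropenia it interrupts PDR001 until grade 2 or lower, or baseline, and then restarts it at a first or second occurrence. Its time limit reads "AE resolution to ≤ Grade 2 or baseline must occur within a maximum period of 12 weeks since Grade 3 or 4 event". The same recovery grade applies to grade 3 thrombocytopenia with clinically significant bleeding and to grade 4 thrombocytopenia.

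Table 6-4 (skin) tells sites to continue PDR001 for grade 2 rash. The same cell adds that resolution to grade 1 or lower, or baseline, "must occur within a period of 12 weeks since Grade 2 event has been identified, otherwise PDR001 must be permanently discontinued".

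**The concern.** The general rule and Table 6-11 both bind the site, both run for 12 weeks, and both apply to a suspected cytopenia. They differ on the grade that counts as recovered. A patient whose count settles at grade 2 has recovered under one and not under the other, and the actions that follow are restart and permanent discontinuation.

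The clock start also differs between places. The general rule counts from a grade that requires interruption. The grade 2 rash row counts from identification of an event that requires no interruption. For a suspected event that is not immune-related, the general rule applies but gives no start date.

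Two sites reading different pages could treat the same patient differently. The SAP summarizes interruptions and permanent discontinuations (2.4.1) and names adverse events leading to discontinuation as a key safety analysis (2.2.1). Protocol 10.5.3.6 uses interruptions to assess tolerability. Those summaries would partly reflect which instruction was followed. Protocol section 12 permits no authorized deviations, so a site cannot settle the matter by agreement.

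**Working it through.** No sample size, power or error rate is involved. The check sets the passages side by side and traces example patients. The general rule's wording about something occurring within 12 weeks is read as: not recovered by the end of 12 weeks.

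| | Protocol 6.3.1.1 | Table 6-11, neutropenia grade 3/4 | Table 6-4, grade 2 rash |
|---|---|---|---|
| Scope | All suspected events | Suspected hematologic events | Immune-related rash |
| Dosing meanwhile | Not stated | Interrupt | Continue |
| Recovered at | Grade 1 or lower, or baseline | Grade 2 or lower, or baseline | Grade 1 or lower, or baseline |
| Clock starts | irAE reaches an interrupting grade | Grade 3 or 4 event identified | Grade 2 event identified |
| If not recovered by 12 weeks | Permanent stop | Permanent stop | Permanent stop |

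**Case 1, recovery grade.** Neutropenia is grade 3 at week 0, grade 2 from week 4, and still grade 2 at week 12. It is a first occurrence, treated as immune-related.
- Table 6-11: recovered at week 4, so restart. The 12-week test is met (4 < 12).
- 6.3.1.1: grade 3 requires interruption, so the clock starts at week 0. Grade 2 is above grade 1, so permanent stop at week 0 + 12 = week 12.

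The case uses grade 3 because 6.3.1.2.1 separately requires permanent discontinuation for any grade 4 irAE.

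**Can the words on baseline reconcile them?** Inclusion criterion 12 requires neutrophils of at least 1.5 and platelets of at least 75 x 10^9/L at screening. In SAP Table 5-3, grade 2 begins below 1.5 for neutrophils and below 75.0 for platelets. A patient who meets the entry limits is therefore at grade 1 or better, and a return to baseline is not a return to grade 2. The one exception would be a count that fell between screening and first dose.

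**Case 2, clock start.** Rash is grade 2 from week 0, does not resolve, and never reaches grade 3.
- Table 6-4: permanent stop at week 12.
- 6.3.1.1: no interruption is required, so its clock never starts. It gives no order either way.

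**Case 3, clock start.** Rash is grade 2 at week 0, grade 3 at week 10, and does not resolve.
- Table 6-4, grade 2 row: week 12.
- 6.3.1.1: week 10 + 12 = week 22.

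**Precedence.** The only deferral to the tables in 6.3.1.1 is inside the steroid condition. It is not attached to the recovery grade or to the clock sentence. Section 6.3.1.3 says that Tables 6-11 and 6-12 serve events without specific requirements elsewhere in the protocol; it does not say that they displace 6.3.1.1.

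**The case against.** The best reply is that a specific table overrides a general instruction. Section 6.3.1.1 is labeled as general, and Table 6-11 is the stated requirement for these events. The parenthesis in the steroid condition also helps this reading. No mandatory column in Tables 6-2 to 6-12 gives a different numeric steroid threshold, so a steroid-only reading leaves the phrase little to refer to. This makes a table-first reading plausible. It does not make it the stated rule, and one sentence would settle it.

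A second reply is that case 1 is fully specified only if the neutropenia counts as an irAE. That is correct. For a non-immune cytopenia the recovery grades still conflict, but 6.3.1.1 supplies no date from which to count.

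A third reply is that the event is rare. The suspected grade 3/4 events listed for 160 first-in-human patients and for 32 nasopharyngeal patients (Protocol 1.2.1.2) include neither neutropenia nor thrombocytopenia. Nor do the most common grade 3/4 events at this study's interim analysis. The count must also remain at grade 2 through week 12. This stands, and it limits the practical size of the problem.

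A reader might infer more from Table 6-4 than it supports.
- **That a patient with grade 2 rash is ordered both to stay on and to come off.** Section 6.3.1.1 never orders anyone to stay on. The instruction to continue and the 12-week limit share one Table 6-4 cell and can be read in sequence, so a site can comply with both passages.
- **That the two columns of the grade 2 rash row conflict.** The phrase "consider dose interruption until tolerable or recovery to grade ≤1 or baseline" is in the recommended column, and 6.3.1.2.1 says which column binds.
- **That a tolerable grade 3 rash has no time limit, because its row counts "within a period of 12 weeks since intolerable Grade 3 event has been identified".** Any grade 3 rash requires interruption, which starts the 6.3.1.1 clock, and 6.1.1 caps interruption at 12 weeks.

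**Conclusion.** The point holds as an internal inconsistency between mandatory instructions; it is not a dispute about a design choice. The main defect is the recovery grade: grade 1 or lower in 6.3.1.1 against grade 2 or lower in Table 6-11, with no stated precedence. For a suspected neutropenia or thrombocytopenia within Table 6-11 that settles at grade 2 through week 12, one rule restarts PDR001 and the other ends it. This assumes that the patient met the entry limits at baseline and, for a definite week-12 date, that the event is treated as immune-related.

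The secondary defect is the clock start. It is undefined in 6.3.1.1 for non-immune events, and it differs between 6.3.1.1 and the grade 2 rash row. In case 3 the two dates are 22 - 12 = 10 weeks apart.

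The number of patients affected cannot be computed, because grade-specific rates of these events are not given; the reported lists suggest that it is small. The exposed results are the discontinuation and interruption summaries. Nothing in the documents shows an effect on the response-rate analysis.

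**What to change.** Reconcile 6.3.1.1 with Tables 6-11 and 6-4. Add one sentence to 6.3.1.1 stating whether the recovery grade and clock start given in a table override the general rule. State when the 12 weeks begin for suspected events that are not immune-related. Align the clock wording of the grade 2 rash row with whatever is decided. Which recovery grade and which clock start apply is for the sponsor's clinical team.

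The cost is a precedence sentence, a clause on clock start and a wording change in Table 6-4, with no added visits or procedures.

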6.3.1.2 Dose Modification requirements for potential immune-mediated adverse events

6.3.1.2.1 Identification of and management requirements for AEs of potential immune-mediated etiology (irAE)

Adverse events of special interest (AESI) include AEs of a potential immune-mediated etiology (irAE) that are associated with PDR001 treatment. An irAE may be experienced by patients treated with PDR001 due to its mechanism of action; it is predicted based on the reported prior experience with other immunotherapies that have a similar mechanism of action. Investigators

must be vigilant and must carefully identify AEs that may be suggestive of potential irAEs as their appearance may be sub-clinical and early diagnosis is critical for its adequate management and resolution.

irAEs are typically low grade and self-limited, often occurring after multiple doses, and most frequently involving the GI tract (diarrhea/colitis), skin (rashes), liver (hepatitis), lung (pneumonitis), kidneys (nephritis) and endocrine systems (a variety of endocrinopathies) and rarely CNS (encephalitis). Serological, immunological and histological assessments should be performed as deemed appropriate by the investigator, to verify the potential immune-related nature of the AE, and exclude a neoplastic, infectious or metabolic origin of the AE.

[figure not shown]
Severe grade or persistent lower grade irAEs typically require interrupting or permanently discontinuing treatment and administration of systemic steroids or other non-corticosteroid immunosuppressive medication when systemic steroids are not effective. Early recognition of irAEs and initiation of treatment are critical to reduce the risk of complications, since the majority of irAEs are reversible with the use of steroids and other immune suppressants.

Patients should be instructed to return to the study site as soon as possible (instead of waiting for their next scheduled visit) if they experience symptoms consistent with an irAE. Patients who experience a new or worsening irAE should be contacted and/or evaluated by the study site more frequently.

Based on literature from compounds with similar mechanism of action of PDR001, instructions have been developed regarding how to identify, assess severity and manage irAEs that may occur in patients receiving PDR001. The dose modification requirements and AE management guidelines for the potential irAEs are provided in the following tables: diarrhea/colitis ([Table 6-2](#)), hepatitis (liver laboratory alterations) ([Table 6-3](#)), skin (rash) ([Table 6-4](#)), nephritis ([Table 6-5](#)), pneumonitis ([Table 6-6](#)), encephalitis ([Table 6-7](#)), endocrinopathies ([Table 6-8](#)), PDR001-infusion reaction & cytokine release syndrome ([Table 6-9](#)), and other potential immune-related AEs of special interest ([Table 6-10](#)). Any grade 4 irAE must result in permanent discontinuation of PDR001.

Under the category of OTHERS ([Table 6-11](#) and [Table 6-12](#)) are included several irAE of interest that must be managed specifically and for which not specific guidance are provided in the table below. OTHERS include (but is not restricted to) the following events: autoimmune neuropathy, demyelinating polyneuropathy, Guillain-Barre, myasthenia Gravis-like syndrome, non-infectious myocarditis, non-infectious pericarditis, pancreatitis and rapid onset of grade 3 fatigue in the absence of disease progression.

Patients receiving PDR001 may experience irAEs other than those listed in this document; therefore, all AEs of unknown etiology associated with drug exposure should be evaluated to determine if they are possibly immune-related. In cases where the specific irAEs are not listed in the tables below, the investigator should follow the dose modification requirements in [Section 6.3.1.3](#) which details the measures to be taken for suspected (they could be potentially immune-related or non-immune-related) AEs. Investigators are encouraged to contact the sponsor as needed to discuss cases that warrant separate discussion outside of the scope of the current instructions.

The dosing modification requirements are mandatory; however, the AE management guidelines are recommendations and can be modified according to local practices. The management of irAEs may include initiation of antibiotics for prophylaxis against opportunistic infections.

Table 6-2 Mandatory dose modification requirements and recommended clinical management guidelines for potential immune-related diarrhea/colitis

Diarrhea/Colitis (NCI-CTCAE v4.03)		
Grade	Recommended Adverse Event management guidelines	Mandatory Dose Modification requirements
Grade 1 (< 4 bowel actions per day over baseline) mild Grade 2 (4-6 bowel actions per day over baseline) and / or abdominal pain/ blood in stool.	
 ● Diet ● Hydration ● Loperamide: initially 4 mg, followed by 2 mg every four hours or after every unformed stool; maximum 16 mg/day. Continue until diarrhea free for 12 hours; ● Diarrhea > 24h: loperamide 2 mg every two hours; maximum 16 mg/day. Consider adding oral antibiotics. ● Diarrhea > 48hrs: loperamide 2 mg every two hours; maximum 16 mg/day. Consider other second-line therapies for diarrhea (e.g: (octreotide, oral diphenoxylate) and oral antibiotics ● If Grade 2 and no improvement in 5 days may require oral steroids ● If Grade 2 diarrhea persists >1 week consider GI consultation and endoscopy to evaluate for colitis. ● If Grade 2 persists for 5 days and worsening of symptoms or diffuse ulcerations and bleeding seen on endoscopy, commence steroids at a dose of 0.5-1mg/kg per day of prednisolone (or IV equivalent) and continue until symptoms improve to Grade 1. If no improvement occurs, manage as per Grade 3. Steroids can be tapered as per Section 6.3.1.2.2. ● Sigmoidoscopy and biopsy can be considered and may assist in determining the duration of steroid taper based on the evidence of macroscopic and microscopic inflammation. 	
 ● Continue PDR001 treatment ● If diarrhea is Grade 2, despite loperamide at 2 mg every two hours for > 48hrs: 
 ● Interrupt PDR001 until diarrhea recovers to Grade ≤1 and then restart PDR001 treatment at the same dose and schedule.
Grade 3 Diarrhea: Increase of ≥7 stools per day over baseline; incontinence; hospitalization indicated; limiting self-care ADL; Grade 3 Colitis: Severe abdominal pain; change in bowel habits; medical intervention indicated; peritoneal signs	
 ● Clinical evaluation and hospitalization mandatory; rule out bowel perforation and intravenous hydration. ● Consider consultation with gastroenterologist and confirmation biopsy with endoscopy. ● In addition to symptomatic treatment (diet, hydration, loperamide, antibiotics if indicated); initiate immediate treatment with intravenous steroids (methylprednisolone 125 mg) followed by high dose oral steroids (prednisone 1 to 2 mg/kg once per day or dexamethasone 4 mg every 4 hours) is recommended. ● When symptoms improve to ≤Grade 1, steroid taper should be done as per Section 6.3.1.2.2. ● Taper over 6 to 8 weeks in patients with diffuse and severe ulceration and/or bleeding. ● If no improvement in 2-3 days: consider initiating infliximab 5mg/kg and continue steroids. (Infliximab is contraindicated in patients with sepsis or a perforation). Upon symptomatic relief initiate a prolonged steroid taper over 45 to 60 days. ● If symptoms worsen during steroid reduction, initiate a re-tapering of steroids starting at a higher dose of 80 or 100 mg followed by a more prolonged taper and administer infliximab. 	
1st occurrence:
 
 ● Interrupt PDR001 until diarrhea/colitis recovers to Grade ≤1 or baseline 
 ● Once recovered restart PDR001 treatment at the same dose and schedule and after appropriate steroid tapering (if initiated). ● AE resolution to ≤ Grade 1 or baseline must occur within a period of 12 weeks since a Grade 3 event has been identified, otherwise PDR001 must be permanently discontinued 
2nd occurrence: Permanently discontinue PDR001

Diarrhea/Colitis (NCI-CTCAE v4.03)		
Grade	Recommended Adverse Event management guidelines	Mandatory Dose Modification requirements
	
 If symptoms persist despite the above treatment a surgical consult should be obtained. 	
Grade 4: Life-threatening consequences; urgent intervention indicated	Same as Grade 3	Permanently discontinue PDR001

Table 6-3 Mandatory dose modification requirements and recommended clinical management guidelines for potential immune-related liver laboratory alterations

Abnormal liver function tests		
Severity	Recommended Adverse Event management guidelines	Mandatory Dose Modification requirements
Grade 2: AST or ALT > 3x ULN to ≤ 5.0x ULN and/or bilirubin > 1.5x ULN to ≤ 3x ULN (if patient meets criteria for Hy's law, refer to Section 6.3.3.1)	Monitor hepatic laboratory tests more frequently (every 2-3 days) until returned to baseline values	
 Interrupt PDR001 treatment until recovery to Grade ≤1 or baseline** 
 Once recovered restart PDR001 treatment at the same dose and schedule
Grade 3 or 4: AST or ALT >5.0xULN and/or bilirubin > 3.0x ULN	
 Monitor hepatic laboratory tests more frequently (every 2-3 days) until returned to baseline values. Consider appropriate consultation* with hepatologist and liver biopsy to establish etiology of hepatic injury, if necessary If after 2-3 days new liver assessment shows worsening of laboratory test consider to initiate treatment with steroids prednisolone 1-2 mg/kg/day or IV equivalents. Add prophylactic antibiotics for opportunistic infections When symptoms improve to Grade ≤1, a steroid taper with dexamethasone 4 mg every 4 hours or prednisone at 1 to 2 mg/kg should be started and continued over no less than 4 weeks. If serum transaminase levels do not decrease 48 hours after initiation of systemic steroids, oral mycophenolate mofetil 500 mg every 12 hours may be given. Infliximab is not recommended due to its potential for hepatotoxicity 	Permanently discontinue PDR001**

* Send viral serology looking for hepatitis A, B, C & CMV and rule out any potential cause of liver injury (i.e. alcohol, other medications, etc.)

**For patients with liver metastasis who begin treatment with grade 2 AST or ALT, if AST or ALT increase by 2 times relative to baseline and last for at least 1 week then the patient should be discontinued

Note: For additional information on follow-up of potential drug induced liver injury cases, refer to [Section 6.3.3.1](#).

Table 6-4 Mandatory dose modification requirements and recommended clinical management guidelines for potential immune-related skin events

Rash Events (NCI-CTCAE v4.03)		
Grade	Recommended Adverse Event management guidelines	Mandatory Dose Modification requirements
Grade 1: Rash covering < 10% Body Surface Area (BSA)	
 ● Initiate prophylactic and symptomatic treatment measures. ● Consider use of topical corticosteroids or urea containing creams in combination with oral antipruritics or moderate strength topical steroid (hydrocortisone 2.5% cream or fluticasone propionate 0.5% cream) ● Reassess after 2 weeks. 	Continue PDR001 treatment
Grade 2: 10-30% of BSA	
 ● If tolerable, treat as per Grade 1; ● If intolerable, initiate systemic steroids (e.g. oral prednisolone 0.5-1mg/kg daily) and consider dose interruption until tolerable or recovery to grade ≤1 or baseline; once recovered, resume PDR001 treatment at the same dose and schedule. ● If symptoms persist or recur consider skin biopsy. 	
Continue PDR001 treatment
 
AE resolution to ≤1 or baseline must occur within a period of 12 weeks since Grade 2 event has been identified, otherwise PDR001 must be permanently discontinued.

Grade 3: More than 30% of BSA	
 ● Obtain a skin biopsy and dermatology consult. ● Initiate systemic steroids with 1mg/kg of prednisolone or IV equivalent. 	
1st occurrence:
 
 ● Interrupt PDR001 until rash recovers to Grade ≤1 or baseline ● Once recovered restart PDR001 treatment at the same dose and schedule 
AE resolution to ≤ Grade 1 or baseline must occur within a period of 12 weeks since intolerable Grade 3 event has been identified. Otherwise, PDR001 must be permanently discontinued
 
2nd occurrence: Permanently discontinue PDR001

Grade 4: Life-threatening	Same as Grade 3	Permanently discontinue PDR001
Other skin events		
Stevens-Johnson syndrome and toxic epidermal necrolysis	Institute supportive care as per institutional guidelines	Permanently discontinue PDR001

Table 6-5 Mandatory dose modification requirements and recommended clinical management guidelines for potential immune-related nephritis

Nephritis (NCI-CTCAE v4.03)		
Grade	Recommended Adverse Event management guidelines	Mandatory Dose Modification requirements
Grade 1: Creatinine >ULN to ≤1.5x ULN)	
 • Monitor creatinine weekly • If creatinine return to baseline resume routine creatinine monitoring per protocol • Promote hydration and cessation of nephrotoxic drugs 	Continue PDR001 treatment
Grade 2: Creatinine >1.5 to ≤3 x ULN	
 • Monitor creatinine every 2 to 3 days • Initiate 0.5 to 1 mg/kg/day prednisone equivalents • If worsening or no improvement: 1 to 2 mg/kg/day prednisone equivalents • Consult with specialist and consider renal biopsy 	
 • Interrupt PDR001 until serum creatinine recovers to ≤ Grade 1 or baseline. 
 • Once recovered restart PDR001 treatment at the same dose and schedule 
AE resolution to ≤ Grade 1 must occur within a period of 12 weeks since Grade 2 event has been identified, otherwise PDR001 must be permanently discontinued.

Grade 3: Creatinine >3.0 to ≤6 x ULN	
 • Monitor creatinine every 1 to 2 days • Start 1 to 2 mg/kg/day prednisone equivalents • Consult with nephrologist 	
1st occurrence:
 
 • Interrupt PDR001 until serum creatinine recovers to ≤Grade 1 or baseline. 
 • Once recovered restart PDR001 treatment at the same dose and schedule 
AE resolution to ≤ Grade 1 or baseline must occur within a period of 12 weeks since the Grade 3 event has been identified, otherwise PDR001 must be permanently discontinued
 
2nd occurrence: Permanently discontinue PDR001.

Grade 4: Creatinine >6x ULN	
 • Monitor creatinine daily • Initiate steroids with 1 to 2 mg/kg/day prednisone or equivalent • Consult with nephrologist and consider renal biopsy 	Permanently discontinue PDR001

Table 6-6 Mandatory dose modification requirements and recommended clinical management guidelines for potential immune-related pneumonitis

Pneumonitis (NCI-CTCAE v4.03)		
Grade	Recommended Adverse Event management guidelines	Mandatory Dose Modification requirements
Grade 1: Radiographic changes only- Asymptomatic	
 • CT scan (high-resolution with lung windows) recommended, with serial imaging to monitor for resolution or progression- re-image at least every 3 weeks • Monitor for symptoms every 2-3 days - Clinical evaluation and laboratory work- 	
 • Interrupt PDR001 until recovery to baseline. 
 • Once recovered, restart PDR001 treatment at the same dose and schedule 
If worsens, treat as Grade 2 or 3-4.

Pneumonitis (NCI-CTCAE v4.03)		
Grade	Recommended Adverse Event management guidelines	Mandatory Dose Modification requirements
	
 up for infection Monitoring of oxygenation via pulse oximetry recommended Consultation of pulmonologist recommended 	AE resolution to ≤ Grade 1 or baseline must occur within a period of 12 weeks since Grade 1 event has been identified, otherwise PDR001 must be permanently discontinued
Grade 2: Symptomatic-medical intervention indicated; limits instrumental ADLs	
 CT scan (high-resolution with lung windows) Monitor symptoms daily, consider hospitalization Clinical evaluation and laboratory work up for infection Consult pulmonologist Pulmonary function tests - if normal at baseline, repeat every 8 weeks Bronchoscopy with biopsy and/or BAL recommended Symptomatic therapy including corticosteroids if clinically indicated (systemic corticosteroids at a dose of 1 to 2 mg/kg/day prednisone or equivalent as clinically indicated). 	
1st occurrence:
 
 Interrupt PDR001 until recovery to Grade ≤1 or baseline 
 Once recovered restart PDR001 treatment at the same dose and schedule 
AE resolution to ≤ Grade 1 or baseline must occur within a period of 12 weeks since Grade 2 event has been identified, otherwise PDR001 must be permanently discontinued.
 
If worsens treat as Grade 3 or 4
 
2nd occurrence: Permanently discontinue PDR001 treatment

Grade 3: Severe symptoms; limits self-care ADLs; oxygen indicated	
 CT scan (high-resolution with lung windows) Clinical evaluation and laboratory work-up for infection Consult pulmonologist 	Permanently discontinue PDR001
Grade 4: Life-threatening respiratory compromise	
 Pulmonary function tests-if < normal, repeat every 8 weeks until ≥ normal Bronchoscopy with biopsy and/or BAL if possible Treat with intravenous steroids (methylprednisolone 125 mg) as indicated. When symptoms improve to ≤ Grade 1, a high dose oral steroid (prednisone 1 to 2 mg/kg once per day or dexamethasone 4 mg every 4 hours). If IV steroids followed by high dose oral steroids does not reduce initial symptoms within 48 to 72 hours, consider non-corticosteroid immunosuppressive medication. 	

Table 6-7 Mandatory dose modification requirements and recommended clinical management guidelines for potential immune-related encephalitis

